17. RISKS AND BENEFITS

Participants in this clinical study will be allocated to one of two treatment groups. In any case, they will be receiving an evidence-based treatment program tailored to their condition, overseen by physicians and physical therapists. Participants in the digital care program will be performing the exercise component using a certified medical device for its intended purpose. Therefore, participants are not running additional risks by participating in this study.

Exercise programs can, however, be associated with temporary pain or discomfort as expected from the typical treatment. In the digital care group, pain and fatigue scores will be asked at the end of each session, and this information is relayed to the physical therapist assigned to the participant, who will contact the patient in case of excessive pain or fatigue. In the conventional PT group, sessions will be performed under direct supervision from a physical therapist. In any case, both participants and physical therapists will be instructed to contact the study investigators in case of an adverse event.

As to the benefits, by participating in this study, participants may experience reduction in pain, improvement in function, mood and general well-being. However, the effects may vary from person to person, and therefore substantial improvements cannot be guaranteed.

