- Motion trackers, placed on body segments using Velcro[®] straps. Each motion tracker is placed in a specific position. To assist in the correct placement of the motion trackers, both the trackers and the matching straps are color-coded. The motion trackers' setup varies according to each therapy.
- Mobile App, that comes pre-installed on a tablet, that guides the patient in each exercise session. Before each exercise, the patient is presented with a real-life video and audio explanation of that exercise. The execution interface is subsequently shown. This screen features: a) a progress bar; b) a repetition counter; c) a star counter and d) a timer displaying time left in the exercise. A correct repetition is defined as a movement starting at the baseline and reaching or surpassing the specified target, without violating movement or posture constraints. In case the patient violates a constraint, a message is prompted showing which movement error was performed, so that the patient can correct the movement in the following attempts. For each correct repetition, the patient earns from 1 to 5 stars, depending on the range of motion of that specific movement in comparison to normative values for that movement. At the end of each session, the patient is presented with a summary of the number of completed repetitions and stars, as well as with badges rewarding him for the progresses achieved in each exercise.
- Web-based Portal that allows the clinical team to generate new patient profiles and create exercise sessions for each patient. To prescribe a session, the clinician needs to select the exercises, number of sets and number of repetitions. When a patient performs a session, the results are uploaded to the platform and available for review. Based on this information, the clinical team can edit the parameters of each exercise according to patient performance and progress.

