4.2 WEB PORTAL

Data is secured in transit to SWORD's Application Programming Interface (APIs) due to enforced application of TLS 1.2 or above. Additionally, a web application firewall protects our servers from Cross-site Scripting (XSS) and SQL Injection attacks.

Access to SWORD's Web Portal is provided only to individuals who have a valid work contract with SWORD Health and have a role within the company that allows them to use the platform (i.e. PTs and IT support).

Access control mechanisms ensure that only authorized users have access to PHI and different functions are mapped to different roles within the platform (i.e. IT support personnel only have access to de-identified data).

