14. INTERVENTION

a. Digital program

Patients in the digital intervention group will benefit from an 8-week program composed of therapeutic exercise, education and cognitive behavioural therapy (CBT) program provided by SWORD Health. These patients will be referred to SWORD Health by the investigator who identified the candidate. SWORD Health will then assign a physical therapist to each patient. The physical therapist will contact the patient for onboarding and will manage the case.

Patients in this group will performed home-based rehabilitation sessions using SWORD Phoenix[®], under remote monitoring by a physical therapist. Participants will be provided with a tablet computer with a SWORD mobile app installed, along with two inertial motion trackers (each comprised of a gyroscope, an accelerometer and a magnetometer) to be placed on chest, upper arm and wrist, respectively. These trackers enable precise movement quantification, feeding the mobile app, which guides the patient through the session, providing video and audio instructions before each exercise, as well as real-time audio and video biofeedback during the exercise. On the other end, the clinical teams are allowed to remotely monitor results and prescribe/edit exercise sessions through a web-based portal.

The exercise component will follow the protocol outlined in **Annex 2**, which can however be adapted by the physical therapist to the specific needs of the participant. Participants will be asked to start with three 20 min sessions per week, building gradually to three 30 min sessions per week. Participants will not be excluded from the study in case of lower adherence, but will not be included in the per-protocol analysis if they perform less than 21 sessions over the course of 8 weeks.

Participants in this group will be considered as dropouts if they: a) choose to abandon the study;b) do not engage in any exercise session for at least fourteen consecutive days.

The educational component will be delivered automatically through a smartphone app (available for iOS and Android), and will take the form of small educational texts that will be released

periodically to the participant. This component is not mandatory per protocol, but metrics on user engagement will be measured.

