Participants will be required to complete a questionnaire similar to the baseline assessment, within a 5-day window beginning at the start of week 4. These assessments will include all the information pertaining to the primary and secondary outcomes, except for those that are collected through a face-to-face assessment. These (shoulder range of motion and PROMIS CAT measures) will not be collected on this assessment. Upon completion of this form, participants in the study will receive a stipend of \$25.

Final assessment (8 weeks)

This assessment will involve a face-to-face visit, where the following outcomes will be assessed: a) shoulder Range of Motion; b) PROMIS CAT measures and c) Participant satisfaction (Net Promoter Score). Shoulder Range of Motion and PROMIS CAT measures will be assessed using a similar methodology to the one descried for the baseline assessment.

Participants will also be required to complete a questionnaire similar to the baseline and interim assessments, within a 5-day window beginning at the start of week 4. These assessments will include all the information pertaining to the primary and secondary outcomes, except for those that are collected in the face-to-face visit. Upon completion of this form, participants in the study will receive a stipend of \$25.

Additional measurements of upper limb function and tri-dimensional motion will also be performed at the onsite visit by the clinician, using a motion capture system. These will not be considered in the outcomes of this study, but will be made available for post-hoc analysis.

Engagement assessment

For participants on the digital group, engagement and usage metrics of the educational and CBT components will also be collected automatically.

Additionally, the following activity log will be collected from patient's Electronic medical records and time stamps, as well as paper survey (or, in the case of the digital group, sent to the study coordinator via email, with the participant identified only by the study ID), to be entered into EDC portal by study coordinator:

- 1. Face-to-face visits registry (dates, times and duration)
- 2. Remote sessions registry (dates, times and duration)
- 3. Number and duration of contacts between PT and participant (emails, text messages, phone and videocalls)
- 4. Total time spent on remote monitoring of the patient (digital group only)

Adverse events

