In any event during the course of the study if subjects experience adverse effects of both internal (on-site) and external (off-site) events, a prompt reporting to the UCSF Human Research Protection Program (HRPP)/institutional review board (IRB) and to the sponsor of the study will take place. This includes any unanticipated problems involving risk to subjects noted in the study. The safety plan in IRB will contain protocol to help with communication and procedures that are in place to monitor and report adverse events should they occur. The investigators will accurately document causality assessment to their best knowledge and follow-up of all definite, probable, or unrelated adverse events to the study and safety-related information.

Care continuity

To ensure that quality of care is not compromised throughout the study, all subjects from both

groups will be assessed at the final appointment to determine whether further care is warranted. If subjects require additional physical therapy services or follow-up back to the physician, the primary investigator will coordinate with UCSF physical therapist to ensure continuity of care or proper closure of their care are complete.

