ANNEX 3- CONVENTIONAL PT INTERVENTION PROTOCOL

The co-investigators are encouraged to use the McClure's staged based rehabilitation therapy (STAR) classification (see Table 1) as a *guide* but not necessarily as a prescriptive manner to select interventions. Instead, the co-investigators will reference their use interventions categorized based on commonly practiced in an outpatient physical therapy setting (see Table 2).

McClure's stage-based rehabilitation therapy (STAR) intervention approach is based on the Irritability of the patient's condition. Assessments of symptoms of Irritability are gathered from the patient's history and findings from the examination. Table 1 represents a guided approach to STAR for the chronic shoulder pain population and the type of interventions used. Table 2 describes the type of commonly used physical therapy interventions that could be used in the cohorts.

Guideline to help determine the stage of Irritability is based on both history and examination findings*

High	Moderate	Low
• Pain >= 7/10	• Pain (4-6/10)	• Pain (<= 3/10)
• Consistent night or	• Intermittent night or rest pain	• Absent night or rest pain
resting pain	• Pain at end of range	• Minimal pain with overhead
• Pain before end of range	• AROM and PROM close	• AROM = PROM
• AROM < PROM	• Moderate disability	• Low disability
• High disability		
Approach: Minimize	Approach: Mild-moderate physical	Approach: Mod-high physical
physical stress	stress	stress
• Activity	Basic-level functional	• High-demand functional
modification	activity restoration	activities

*Taken from Staged approach (STAR) for rehabilitation classification by McClure et al.

Table 1. McClure's staged approach to shoulder intervention based on different impairments

Impairments	Irritability	Intervention	Examples of
		Approaches	Intervention**
Restricted passive mobility	Low	• ROM	• Aggressive active and
due to joint/muscle/neural		• Stretching	passive stretches (e.g.,
tissues		• manual therapy:	sleeper stretches;
		tolerable stretch	foam roller T's, Y's,
		sensation at end-	I's; Doorway stretch)
		range	
		Hold longer	
		duration and	
		frequency	
Restricted passive mobility	Moderate	• ROM	• Active and passive
due to joint/muscle/neural		• Stretching	stretches (e.g., gentle
tissues		• Comfortable end-	sleeper stretches;
		range manual	Foam roller T's, Y's,
		therapy	I's; modified to $\frac{1}{2}$ to
			full foam roller T's,
			Y's, I's; Modified
			doorway stretch)

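### Adverse events rest on unsolicited report and are detected differently in the two arms; with no identical adverse-event question at 4 or 8 weeks, counts may be incomplete and are not comparable between arms

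*Combined protocol and SAP*

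**What the plan says.** Section 15 (Adverse events) requires prompt reporting to the IRB and to the sponsor. It makes the investigators responsible for documenting causality and for "follow-up of all definite, probable, or unrelated adverse events to the study and safety-related information". It leaves monitoring and reporting procedures to a safety plan held with the IRB.

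Section 17 gives one reporting route for both arms: participants and physical therapists are told to contact the investigators if an adverse event occurs. The same paragraph describes different observation in each arm. Conventional sessions are directly supervised by a physical therapist. For the digital arm it says "In the digital care group, pain and fatigue scores will be asked at the end of each session", and that "this information is relayed to the physical therapist assigned to the participant, who will contact the patient in case of excessive pain or fatigue". No definition of excessive is given. Section 14 says of the digital arm that "SWORD Health will then assign a physical therapist to each patient".

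Section 15 (Engagement assessment) lists what enters the study database from the activity log. It covers the dates, times and durations of face-to-face visits and remote sessions, the time spent on remote monitoring, and "Number and duration of contacts between PT and participant (emails, text messages, phone and videocalls". For the digital arm the log goes to the study coordinator by email under the study ID.

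The 4- and 8-week questionnaires carry the primary and secondary outcomes of section 8. Adverse events are not among those outcomes, and section 16 does not mention them.

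**The concern.** The investigators must judge causality, yet as described they learn of an event only if someone volunteers it. In the conventional arm, the person placed to volunteer it is watching the participant exercise. In the digital arm, it is the participant at home or a company-assigned therapist reading scores remotely. The most regular symptom record in the trial, the digital per-session scores, has no described path to the people who assess causality, and no stated rule says when a score becomes an adverse-event report.

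What is at stake is any safety statement that sets the arms side by side. Section 17 already says that participants run no additional risks by taking part. A low digital count could readily be taken to confirm this, and a high one to contradict it, when either might partly reflect how each arm is watched. The primary QuickDASH comparison is not affected.

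**Working it through.** The plan states no adverse-event figure, so there is nothing to reproduce. The check sets the text side by side and follows the route from a symptom to the investigator.

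| Step | Digital arm | Conventional arm |
|---|---|---|
| Scheduled sessions (section 14) | 3 per week × 8 weeks = 24, at home | 2 per week × 8 weeks = 16, face to face |
| What brings a problem to light (section 17) | Pain and fatigue score after each session | Direct supervision; no per-session score described |
| Who sees it first (sections 14 and 17) | Company-assigned therapist | Treating physical therapist |
| Other therapist contact (sections 14 and 17) | Therapist contacts the patient if scores are excessive | Secure messages, or calls up to twice per week |
| Route to the investigator (section 17) | Unsolicited report | Unsolicited report |
| Log entries (section 15) | Dates, durations, contact counts, monitoring time | Dates, durations, contact counts |
| Adverse-event question at 4 or 8 weeks (sections 8 and 15) | None listed | None listed |

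The count of 24 uses section 14. Annex 2 heads its tables as daily sessions, and the two places need to be reconciled. The point does not depend on the count.

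Three things follow from the table.

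1. The last formal step is the same in both arms, but it is passive in both.
2. The detection steps before it differ in kind, by observation in one arm and by self-scored symptoms in the other.
3. Nothing collected at the same time and in the same way in both arms asks about adverse events, so no common measure exists on which to compare them.

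To show what unequal capture could do, take 40 participants per arm (section 9), the same true risk p in both arms, and capture proportions of 0.9 and 0.6. Both p and the capture proportions are assumptions, because the documents give neither. Expected recorded cases = 40 × p × capture.

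| Assumed p | Capture 0.9 | Capture 0.6 |
|---|---|---|
| 0.05 | 40 × 0.05 × 0.9 = 1.8 | 40 × 0.05 × 0.6 = 1.2 |
| 0.10 | 40 × 0.10 × 0.9 = 3.6 | 40 × 0.10 × 0.6 = 2.4 |
| 0.20 | 40 × 0.20 × 0.9 = 7.2 | 40 × 0.20 × 0.6 = 4.8 |

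With no true difference, the ratio of recorded cases is 0.9 / 0.6 = 1.5 at every risk level. Nothing in the documents says which arm belongs in which column. Supervision could favour capture in the conventional arm, and a structured symptom question after every session could favour it in the digital arm.

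**The case against.** The strongest reply is that section 15 defers monitoring and reporting procedures to the IRB safety plan. That plan may already contain a solicited question or a rule for passing on scores. This stands, and the conclusion is conditional on it.

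Second, the reporting instruction in section 17 is common to both arms and covers the digital therapist who sees the scores. This also stands: the difference lies in detection, not in the formal route.

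Third, adverse events are not an outcome and no comparison of them is planned. That limits the consequence, but by-arm counts may still be reported and read.

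Fourth, the site does hear from both arms in the same way through the QuickDASH, pain and medication items on the questionnaires, the 8-week visit, and the final review of whether further care is needed. This is fair. A reader might infer that nothing from the digital arm reaches the site, and that would be wrong. These contacts ask about status, however, not about events.

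Other stronger readings are tempting but unsupported:

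- **Scores locked in a closed portal.** Section 4.2 says "Access to SWORD's Web Portal is provided only to individuals who have a valid work contract with SWORD Health", and section 3 says "When a patient performs a session, the results are uploaded to the platform and available for review". Neither names the pain and fatigue scores, and section 17 says only that they are relayed to the therapist. A log-in restriction also does not limit what a therapist may tell the investigator. The text supports only that no transfer is described.
- **Conventional therapists are themselves investigators.** Annex 3 says "the co-investigators will reference their use interventions categorized", which suggests this. Sections 14 and 17 treat physical therapists and investigators as separate roles, so the point does not rest on it.
- **A causality scale with no uncertain category.** The phrase in section 15 reads as a narrative way of covering all events, not as a defined scale.

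**Conclusion.** The point holds as a gap in how adverse events are collected. Both arms depend on unsolicited reports, detection differs by arm, the digital per-session scores have no described transfer to the investigator or the study database, and no identical adverse-event question is listed at 4 or 8 weeks. Adverse-event counts may therefore be incomplete and, as the plan stands, are not comparable between arms.

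A reader might go further and infer that the record will be incomplete, or that digital events will be undercounted. The documents support neither. The safety plan is not available, pain and fatigue scores are not in themselves adverse events (section 17 treats temporary discomfort as expected), and the extra symptom questioning could raise the digital count. The factor of 1.5 above follows from assumed capture rates and is not an estimate. This is a cheap improvement to safety reporting, not a threat to the primary analysis.

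**What to change.** First, add one identical adverse-event question to the 4- and 8-week EDC questionnaires that both arms already complete. It should ask about any new or worsened symptom, any other problem, whether care was sought, and the date. Tabulate the answers by arm. Keep the unsolicited route alongside it, since the question captures only those who return the form. Section 15 places the window for the final questionnaire at the start of week 4, the same as for the interim one. That wording needs to be reconciled with the 8-week assessment so that the second question covers the second half of the program.

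Second, add the per-session pain and fatigue scores and the reason for each safety-related contact to the digital-arm log already sent to the coordinator by study ID. Label these as supporting data for causality assessment, not as a between-arm comparison, because the conventional arm has no counterpart.

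If the IRB safety plan already provides either element, a cross-reference in section 15 is enough for that element.

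The cost is protocol wording, slightly longer forms at two existing time points, a few extra log columns, and more minor events recorded. Participants know their allocation, so a common question makes collection alike but does not remove every difference in how people report.

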18. CONFIDENTIALITY

PHI will be shared with individuals and organizations that conduct or watch over this research, including:

- The research sponsor
- People who work with the research sponsor
- Government agencies, such as the Food and Drug Administration
- The Institutional Review Board (IRB) that reviewed this research

Data used for dissemination of study results will be de-identified before publication.

ANNEX 2- DIGITAL THERAPEUTIC EXERCISE PROTOCOL

Should	ler Pain Exercise Protocol	. Phase 1 (week 1)
Goals		Precautions
Recovery of full range of motion (passive and active) Decrease pain and inflammatory signs Gradually increase muscular strength		Do not perform loaded exercises above 70° flexion / abduction
	Intervention	
	Daily Digital Therapis	t Sessions
	Remote session – Assessn	nent/Deploy
Digital Therapist Exercises	Mobility	Strength 1 (External Load – RPE >8)
	Standing Positio)n
Shoulder Flexion	2 sets of 8 reps (alternating)	2 sets of 8 reps (2/5 lbs.) (alternating)
Shoulder Hyperextension	2 sets of 8 reps (alternating)	
Shoulder Abduction	2 sets of 8 reps (alternating)	2 sets of 8 reps (5/7 lbs.) (alternating)
Scapular Plane Elevation	2 sets of 8 reps (alternating)	2 sets of 8 reps (2/5 lbs.) (alternating)
Diagonal 1 Flexion		
Diagonal 2 Flexion	2 sets of 8 reps (alternating)	2 sets of 8 reps (2/5 lbs.) (alternating)
Shoulder External Rotation	2 sets of 8 reps (alternating)	2 sets of 8 reps – Theraband (alternating)
Shoulder Internal Rotation		
Hand to Back	2 sets of 8 reps (alternating)	
Shoulder Horizontal Abduction		2 sets of 8 reps (alternating)
Shoulder Horizontal Adduction		

Shoulder External Rotation in Abduction		3 sets of 8 reps (5/7 lbs.) (alternating)
Shoulder Internal Rotation in Abduction		
Scapulae Retraction with Shoulder Flexion	2 sets of 8 reps (alternating)	
Scapulae Protraction with Shoulder Flexion		
Arm Circles with Shoulder Flexion		
Arm Circles with Shoulder Abduction		2 sets of 8 reps (2/5 lbs.) (alternating)
Chair Press-Up		
Push-Up Against the Wall		
Pendulum		
Estimated Therapy Time	20 min	20 min

Sh	oulder Pain Exercise	e Protocol. Pha	nse 1 (weeks	2 to 4)
Goals			Precautions	
Recovery of full range of motion (passive and active) Decrease pain and inflammatory signs Gradually increase muscular strength		Do not per	form loaded exercises above 70° flexion / abduction	
]	Intervention		
		ital Therapist S		
	4-Week	Remote Assess		1
Digital Therapist Exercises	Mobility	Strength 1 Load – F		Strength 2 (External Load – RPE >8)
	Star	nding Position		
Forearm Supination	2 sets of 10 reps (alternating)			
Elbow Flexion		2 sets of (alterna		
Shoulder Flexion	2 sets of 10 reps (alternating)	2 sets of 10 lbs.) (alte		
Shoulder Hyperextension	2 sets of 10 reps (alternating)			2 sets of 10 reps – Theraband (alternating)
Shoulder Abduction	2 sets of 10 reps (alternating)	2 sets of 10 lbs.) (alte		
Scapular Plane Elevation	2 sets of 10 reps (alternating)			2 sets of 10 reps (2/5 lbs.) (alternating)
Diagonal 1 Flexion		2 sets of 10 lbs.) (alte		
Diagonal 2 Flexion	2 sets of 10 reps (alternating)			2 sets of 10 reps (2/5 lbs.) (alternating)
Shoulder External Rotation	2 sets of 10 reps (alternating)	2 sets of 1 Theraband (a	-	

Shoulder Internal Rotation	2 sets of 10 reps		3 sets of 8 reps – Theraband
	(alternating)		(alternating)
Hand to Back	2 sets of 10 reps		
	(alternating)		
Shoulder Horizontal		2 sets of 10 reps	
Abduction		(alternating)	
Shoulder Horizontal			2 sets of 10 reps (alternating)
Adduction			2 sets of 10 teps (alternating)
Shoulder External Rotation		2 sets of 10 reps (5/7	
in Abduction		lbs.) (alternating)	
Shoulder Internal Rotation			2 sets of 10 reps (5/7 lbs.)
in Abduction			(alternating)
Scapulae Retraction with	2 sets of 10 reps		
Shoulder Flexion	(alternating)		
Arm Circles with Shoulder		2 sets of 10 reps (2/5	
Flexion		lbs.) (alternating)	
Arm Circles with Shoulder			2 sets of 10 reps (2/5 lbs.)
Abduction			(alternating)
Chair Press-Up			2 sets of 10 reps (alternating)
Push-Up Against the Wall			2 sets of 10 reps (alternating)
Pendulum			
	Ly	ing Position	
		2 sets of 10 reps (2/5	
Shoulder Flexion		lbs.) (alternating)	
Shouldon Entore 1 Detet			2 sets of 10 reps (2/5 lbs.)
Shoulder External Rotation			(alternating)
Shoulder Internal Rotation		2 sets of 10 reps (2/5	
Shoulder Internal Kolatioli		lbs.) (alternating)	
Estimated Training Time	29 min	29 min	28 min

Shoulder	Pain Exer	cise Protoc	ol. Phase 2 (Weeks 5 to 8)	
Goals	Goals		Precautions	
Range of motion conservation				
Global muscular strengthening in asymptomatic range of movement, focusing on: - Rotator cuff - Scapular stabilizers - Deltoids		Do not perform push-ups on the floor in case of complete		
		rotator cuff tears (use inclined planes)		
		Interven	tion	
	Daily I	Digital Ther	apist Sessions	
	8 W	eek Remote	Assessment	
Digital Therapist Exercises	Mobility		Strength 1 (External Load – RPE >8)	Strength 2 (External Load – RPE >8)
		Standing P	osition	
Shoulder Flexion	2 sets of 10 reps (alternating)		2 sets of 10 reps (5/7 lbs.) (alternating)	
Shoulder Hyperextension				2 sets of 10 reps (Theraband) (alternating)
Shoulder Abduction	2 sets of 10 reps (alternating)		2 sets of 10 reps (5/7 lbs.) (alternating)	
Scapular Plane Elevation	2 sets of 10 reps (alternating)			2 sets of 10 reps (5/7 lbs.) (alternating)
Diagonal 1 Flexion	2 sets of 10 reps (alternating)		2 sets of 10 reps (5/7 lbs.) (alternating)	
Diagonal 2 Flexion		of 10 reps mating)		2 sets of 10 reps (5/7 lbs.) (alternating)

Shoulder External Rotation	2 sets of 10 reps (alternating)	2 sets of 10 reps (Theraband) (alternating)	
Shoulder Internal Rotation			2 sets of 10 reps (Theraband) (alternating)
Hand to Back	2 sets of 10 reps (alternating)		
Shoulder Horizontal Abduction		2 sets of 10 reps (Theraband) (alternating)	
Shoulder Horizontal Adduction			2 sets of 10 reps (Theraband) (alternating)
Shoulder External Rotation in	2 sets of 10 reps	2 sets of 10 reps (5/7	
Abduction	(alternating)	lbs.) (alternating)	
Shoulder Internal Rotation in Abduction	2 sets of 10 reps (alternating)		
Scapulae Retraction with Shoulder Flexion	2 sets of 10 reps (alternating)		
Scapulae Protraction with Shoulder Flexion			
Arm Circles with Shoulder Flexion		2 sets of 10 reps (5/7 lbs.) (alternating)	
Arm Circles with Shoulder Abduction			2 sets of 10 reps (5/7 lbs.) (alternating)
Chair Press-Up			2 sets of 10 reps (consecutive)
Push-Up Against the Wall			2 sets of 10 reps (alternating)
Pendulum			

Lying Position			
Shoulder Flexion		2 sets of 10 reps (5/7	
		lbs.) (alternating)	
Shoulder Abduction		2 sets of 10 reps (5/7	
		lbs.) (alternating)	
Shoulder External Rotation			
Shoulder Internal Rotation			
Shoulder Horizontal Abduction			2 sets of 10 reps (5/7
			lbs.) (alternating)
Arm Circle with Shoulder		2 sets of 10 reps (5/7	
Flexion		lbs.) (alternating)	
Arm Circle with Shoulder			2 sets of 10 reps (5/7
Abduction			lbs.) (alternating)
Estimated Training Time	29 min	29 min	27 min

